10.3.1 Anticipated mortality

There are few data available to guide mortality assumptions. In an international registry of valve-in-valve TAVR, the short-term (30-day) mortality of coronary obstruction complicating TAVR was 50%, despite coronary stenting {Ribeiro, 2017 #362183}. The long-term mortality is expected to be larger. There is no registry of subjects not offered valve-in-valve TAVR because of threatened coronary obstruction.

Absent data, we are forced to use judgement and experience to estimate clinically acceptable mortality for this group of patients with “no good options.” We assume that intentional fracture of surgical bioprosthetic valve frames would confer incremental mortality, although there are no available data. To come to this determination, we polled our lead site investigators, who are selected for their high-volume experience and quality. The best estimate of clinically-acceptable 30-day mortality was 15% for standalone BASILICA and 20% for BASILICA with valve fracture.

10.3.2 Stopping Rules for no intentional overexpansion of bioprosthetic stratum

The study will be monitored to ensure that the mortality within 30-days after the procedure does not substantially exceed an anticipated rate. We anticipate the rate of 30-day mortality is 15% or less and determine the stopping rule by a Bayesian approach [8]. The stopping boundary is reached if the posterior probability that the 30-day mortality rate exceeds 15% is at least 90%. We take our prior distribution to be a beta distribution so that our prior clinical opinion is worth 20% of the weight we will place on the new study data, which gives the prior parameters $a = 0.9$, $b = 5.1$. Hence when we make decisions about stopping the study, the data from the study will dominate over the prior opinion.

The following table summarizes the threshold numbers for the stop rule boundary, which would lead to a recommendation to stop the study due to the excess 30-day mortality.

Number of subjects in the stratum	Stop if the number of deaths within 30 days reaches
2	2
3-6	3
7-11	4
12-16	5
17-21	6
22-26	7
27-30	8

We investigated the performance of the above stopping rule by a simulation study. In each simulation run, we generated a study with 30 independent Bernoulli trials, each with a true certain 30-day mortality, and compared these outcomes with the above stopping boundary to determine whether the study was stopped. We repeated the simulation 100,000 times and computed the proportion of stopped studies using the above stopping rule. The following table summarizes the performance of this stopping rule:

True 30-day mortality rate	10%	15%	20%	25%	30%	35%
Proportion of Stopped Studies	4.8%	17.3%	39%	62.3%	81.3%	92.2%
Average number of subjects	29.1	27	23.5	19.4	15.4	12.1
Average number of 30-day mortality	2.9	4	4.7	4.9	4.6	4.2

These simulation results suggest that our stopping rule has a low probability stopping a study when the true 30-day mortality rate is 15% or less, and the probability of stopping a study is high when the true 30-

day mortality rate exceeds 15%. There, we believe that our Bayesian stopping rule for 30-day mortality has satisfactory statistical properties.

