Exclusion Criteria	
Does not consent to participate
 
Excessive target aortic leaflet calcification or masses on baseline CT
 
Survival despite successful procedure expected < 12 months
 
Subjects unwilling to participate or unwilling to return for study follow-up activities.
 
Pregnancy or intent to become pregnant prior to completion of all protocol follow-up procedures

Phase:	Pilot
Study Procedure	
NHLBI Data Coordinating Center
 
NHLBI + Local Institutional Review Boards
 
Sites are trained by national PIs and NHLBI investigators
 
Subjects are identified by site investigators
 
Baseline and follow-up CT and fluoroscopy are analyzed by core laboratory
 
Subject eligibility is confirmed by local multidisciplinary heart team including cardiac surgery, and is confirmed by study eligibility committee
 
Subjects are enrolled prospectively
 
Primary analysis based on 30-day outcomes; Secondary analysis includes 12-month outcomes

Sample Size	30 subjects at up to 6 sites
Risk-benefit determination	These patients have few or no therapeutic alternatives and have the potential to benefit from this procedure
Number of Sites enrolling participants:	6
Study Duration:	Two years
Participant Duration:	One year

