10.0 BIOSTATISTICAL AND ANALYTICAL CONSIDERATIONS

10.1 Sample Size

The sample size is not statistically derived. This is a safety and feasibility study that enables patient access to a novel medical procedure, when these patients have no other good medical options to treat symptomatic aortic valve failure.

Up to 60 subjects will be consented until 30 subjects undergo attempted BASILICA TAVR in this protocol.

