10.3 Stopping Rules and Data Safety Monitoring

A Data and Safety Monitoring Board (DSMB) appointed by the NHLBI Division of Intramural Research will monitor the safety of subjects in the study as described in the investigational plan. All members of the DSMB are unaffiliated to the study. The NHLBI DSMB will review the protocol progress report at six month intervals, or more frequently upon request of PI, IRB, and/or NHLBI Clinical Director. The DSMB may recommend early termination of the study for considerations of safety and efficacy. Unanticipated Adverse Device Effects (UADEs) will be submitted to the DSMB following the same timelines as the IRB (See section 9.2.4).

In the case of death or serious UADE, if the sponsor and the principal investigator determine that the event presents an unreasonable risk to the participating subjects, the clinical trial will be terminated within 5 working days after making that determination and not later than 15 working days after the sponsor first receives notice of the effect. [21 CFR 812.46]. All clinical sites will be notified of this action.

Each institutional IRB will review all Serious Adverse Events, Unanticipated Adverse Device Effects, and Unanticipated Problems, and may choose to suspend or terminate the protocol based on those findings. We believe this will protect subject safety.

We propose different stopping rules based on whether the operator elects intentionally to over-expand the bioprostheses.

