10.3.3 Stopping Rules for intentional overexpansion of bioprosthetic stratum

The study will be monitored to ensure that the mortality within 30-days after the procedure does not substantially exceed an anticipated rate. We anticipate the rate of 30-day mortality is 20% or less and determine the stopping rule by a Bayesian approach [8]. The stopping boundary is reached if the posterior probability that the 30-day mortality rate exceeds 20% is at least 90%. We take our prior distribution to be a beta distribution so that our prior clinical opinion is worth 20% of the weight we will place on the new data. This gives the prior parameters $a = 1.2$, $b = 4.8$. Hence when we make decisions about stopping the study, the data from the study will dominate over the prior opinion.

The following table summarizes the threshold numbers for the stop rule boundary, which would lead to a recommendation to stop the study due to the excess 30-day mortality.

Number of subjects in the "overexpansion of bioprosthetic stratum"	Stop if the number of deaths within 30 days reaches
3-5	3
6-8	4
9-12	5
13-16	6
17-20	7
21-24	8
25-28	9
29-30	10

We investigated the performance of the above stopping rule by a simulation study. In each simulation run, we generated a study with 30 independent Bernoulli trials, each with a true certain 30-day mortality, and compared these outcomes with the above stopping boundary to determine whether the study was stopped. We repeated the simulation 100,000 times and computed the proportion of stopped studies using the above stopping rule. The following table summarizes the performance of this stopping rule:

True 30-day mortality rate	10%	15%	20%	25%	30%	35%	40%
Proportion of Stopped Studies (%)	1.6%	6.9%	18.9%	38.3%	60.5%	78.5%	90.5%
Average number of subjects	29.6	28.7	26.7	23.6	19.7	16	12.7
Average number of 30-day mortality	3	4.3	5.3	5.9	5.9	5.6	5.1

These simulation results suggest that our stopping rule has a low probability stopping a study when the true 30-day mortality rate is 20% or less, and the probability of stopping a study is high when the true 30-day mortality rate exceeds 20%. There, we believe that our Bayesian stopping rule for 30-day mortality has satisfactory statistical properties.

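### Each stopping-rule performance table, and each 20% prior weight, assumes 30 subjects in its own stratum, but the whole trial has 30; whole-study stopping probability is not given

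*Combined protocol and SAP*

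**What the plan says.** The Protocol Summary (1.0) gives the size as "30 subjects at up to 6 sites". Section 10.1 says the same: "Up to 60 subjects will be consented until 30 subjects undergo attempted BASILICA TAVR in this protocol".

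Section 10.3 divides these subjects into two exclusive groups: "We propose different stopping rules based on whether the operator elects intentionally to over-expand the bioprostheses". Section 10.3.1 explains why the limits differ (15% without valve fracture, 20% with it): "We assume that intentional fracture of surgical bioprosthetic valve frames would confer incremental mortality".

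Section 10.3.2 covers subjects without intentional over-expansion (called standard below). It uses a Beta(0.9, 5.1) prior and a 15% limit, and describes its check as follows: "In each simulation run, we generated a study with 30 independent Bernoulli trials, each with a true certain 30-day mortality". Section 10.3.3 covers over-expansion, with a Beta(1.2, 4.8) prior and a 20% limit, and again says "we generated a study with 30 independent Bernoulli trials". Each section prints boundaries for up to 30 subjects in its stratum.

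On the prior, 10.3.2 says "prior clinical opinion is worth 20% of the weight we will place on the new study data", and 10.3.3 says the same in nearly the same words. Both add that the data will dominate. In both sections a crossing is something "which would lead to a recommendation to stop the study due to the excess 30-day mortality". Both conclude that stopping is unlikely at or below the limit and highly likely above it.

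**The concern.** A subject belongs to one stratum only, so the two stratum sizes sum to 30. Two tables that each assume 30 in their own stratum describe a trial of 60. At most one can apply, and only if the other stratum is empty. The 20% prior weight has the same problem.

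The DSMB and IRBs will read these tables as the performance of the mortality guard. A smaller stratum gives its rule fewer chances to fire, so detection within it is lower than printed. Two rules that can each stop the study also raise the overall chance of a false stop, and neither section reports that chance. The separate over-expansion rule exists because extra mortality is expected there, so harm confined to that stratum is a case it must catch.

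**Working it through.** **Inputs.** Total of 30 (1.0, 10.1). Priors, limits, the 90% posterior threshold, boundaries and performance tables (10.3.2, 10.3.3). The documents give no split between strata, so the splits below are assumptions and a range is shown.

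**1. Boundaries.** After *x* deaths in *n* subjects the posterior is Beta(*a* + *x*, *b* + *n* − *x*). The boundary is the smallest *x* with P(rate > limit) ≥ 0.90. For the 15% rule at *n* = 30, *x* = 7 gives 0.846 and *x* = 8 gives 0.925, so the boundary is 8, as printed. Every row of both boundary tables reproduces. The boundary at a given *n* does not depend on the final stratum size.

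**2. The plan's own performance figures.** Let *f*ₙ(*d*) be the probability of *d* deaths after *n* subjects without having stopped. Then *f*ₙ(*d*) = (1 − *p*) *f*ₙ₋₁(*d*) + *p* *f*ₙ₋₁(*d* − 1). Any probability at or above the boundary is moved to the stopping total. The check is made after every subject. Run to *n* = 30:

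| True rate | 10% | 15% | 20% | 25% | 30% | 35% | 40% |
|---|---|---|---|---|---|---|---|
| 15% rule, printed | 4.8 | 17.3 | 39 | 62.3 | 81.3 | 92.2 | – |
| 15% rule, exact | 4.8 | 17.5 | 38.9 | 62.4 | 81.0 | 92.2 | – |
| 20% rule, printed | 1.6 | 6.9 | 18.9 | 38.3 | 60.5 | 78.5 | 90.5 |
| 20% rule, exact | 1.6 | 6.9 | 19.2 | 38.5 | 60.2 | 78.5 | 90.5 |

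All 13 values agree within 0.4 points, so both tables were computed for 30 subjects per stratum.

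**3. Prior weight.** 0.9 + 5.1 = 6 and 1.2 + 4.8 = 6. A weight of 20% requires *n* = 6 / 0.20 = 30. In general the weight is 6/*n*.

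**4. Each rule in a smaller stratum** (same recursion, ended at *n*; stopping probability in %):

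| *n* | Prior weight 6/*n* | 15% rule, true 15% | 15% rule, true 30% | 20% rule, true 20% | 20% rule, true 30% | 20% rule, true 40% |
|---|---|---|---|---|---|---|
| 30 | 20% | 17.5 | 81.0 | 19.2 | 60.2 | 90.5 |
| 25 | 24% | 16.0 | 75.4 | 17.6 | 54.7 | 86.0 |
| 20 | 30% | 14.1 | 67.6 | 15.9 | 49.0 | 80.6 |
| 15 | 40% | 11.5 | 56.6 | 12.5 | 38.4 | 68.3 |
| 10 | 60% | 8.2 | 40.9 | 8.7 | 25.8 | 49.2 |
| 5 | 120% | 4.0 | 19.4 | 5.8 | 16.3 | 31.7 |

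One entry can be checked by hand. With five over-expansion subjects the boundary is 3 deaths throughout, so at a true 40% the result is P(at least 3 of 5) = 10(0.4³)(0.6²) + 5(0.4⁴)(0.6) + 0.4⁵ = 0.2304 + 0.0768 + 0.0102 = 31.7%.

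**5. Chance that at least one rule fires.** For independent strata this is 1 − (1 − P_standard)(1 − P_over-expansion). At 15/15 with both at their limits: 1 − (1 − 0.115)(1 − 0.125) = 22.6%. Splits are standard/over-expansion; results in %, from unrounded values:

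| True rates (standard / over-expansion) | 25/5 | 20/10 | 15/15 | 10/20 | 5/25 | Printed, single rule |
|---|---|---|---|---|---|---|
| 15% / 20% (both at limit) | 20.9 | 21.6 | 22.6 | 22.8 | 20.9 | 17.3; 18.9 |
| 25% / 30% | 63.7 | 62.5 | 63.1 | 63.3 | 60.5 | 62.3; 60.5 |
| 30% / 35% | 81.2 | 79.6 | 80.0 | 80.2 | 78.0 | 81.3; 78.5 |
| 15% / 40% (over-expansion only) | 42.7 | 56.4 | 71.9 | 82.2 | 86.6 | 90.5 |
| 15% / 30% (over-expansion only) | 29.7 | 36.2 | 45.5 | 53.2 | 56.5 | 60.5 |
| 30% / 20% (standard only) | 76.8 | 70.4 | 62.0 | 50.3 | 33.6 | 81.3 |

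The single-harm rows include false stops from the other stratum. In the 42.7% at 25/5, the standard rule alone contributes a 16.0% false-stop chance and the over-expansion rule detects only 31.7%.

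**6. The concluding sentences.** Five points above the limit, the printed stopping probabilities are 39% (15% rule at a true 20%) and 38.3% (20% rule at a true 25%). Neither is high.

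**The case against.** Nothing is miscalculated. The boundaries follow from the priors, the printed proportions reproduce, and each section states openly that it simulated 30. With no split known in advance, 30 is the largest possible stratum, and either table would be right if every subject fell in that stratum. All of this stands, but it does not make both tables true of the same trial.

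The denominator of the 20% is never named, so 30 is an inference. That also stands, though no other size gives 20%. The weight is 6/*n* at every interim look whatever the split, and the claim that the data dominate fails only with six or fewer subjects. The 20% is therefore best read as an end-of-study figure, and as such it is wrong for any stratum smaller than 30.

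The word study is also used in these sections for one simulated stratum, so a crossing might be meant to halt only that stratum. The text should settle this. If it does mean the stratum alone, the joint figures matter less and the figures in step 4 become the relevant ones.

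Whole-study stopping hardly moves when both strata are raised together, low detection with five patients is unavoidable, and the 39% and 38.3% are printed just above the sentences that call stopping likely. Section 10.3 also gives the DSMB discretion to recommend termination, IRB review of serious events, and sponsor termination for unreasonable risk. No boundary decision would change. These points limit the consequence; they do not correct the stated performance.

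**Conclusion.** The concern holds. The two performance tables and the two 20% statements cannot all describe a 30-subject trial. The fault lies in the description of performance, not in the boundaries.

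The error runs in both directions. When both strata are at their limits, whole-study false stopping is about 21% to 23% over the mixed splits examined, against 17.3% and 18.9% printed. When both are raised by the same margin, the printed values are close. When only one stratum is harmful, protection is lower than printed, and the shortfall grows as that stratum shrinks: for over-expansion at 40% with standard at 15%, 42.7% (25/5) to 86.6% (5/25) against 90.5%.

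These figures assume fixed splits, independent strata, and 30-day outcomes known after each subject, as the plan's own simulation implies. If all 30 subjects fell in one stratum, that stratum's table would be correct.

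**What to change.** In 10.3.2 and 10.3.3:

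1. Recompute both performance tables for plausible stratum sizes that sum to 30, for example 25/5, 20/10 and 15/15, and state the expected split if there is one.
2. Add the probability that at least one rule fires with both strata at their limits, both raised, and only one raised.
3. State whether a crossing leads to a recommendation about the stratum or about the whole study.
4. Replace the 20% sentences with a statement that the prior is worth 6 subjects and that its weight relative to the data is 6 divided by the number of subjects in the stratum. Give that weight for the expected sizes, and qualify the claim that the data dominate when a stratum is small.
5. Replace the general claim of high stopping probability above the limits with the computed probabilities.

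The cost is a short computation and some rewording. No boundary, mortality limit or sample size has to change. The reported single-stratum detection will look less favourable, and the whole-study false-stop figure will be about 21% to 23% for mixed splits.

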10.3.3 Stopping Rules for intentional overexpansion of bioprosthetic stratum

The study will be monitored to ensure that the mortality within 30-days after the procedure does not substantially exceed an anticipated rate. We anticipate the rate of 30-day mortality is 20% or less and determine the stopping rule by a Bayesian approach [8]. The stopping boundary is reached if the posterior probability that the 30-day mortality rate exceeds 20% is at least 90%. We take our prior distribution to be a beta distribution so that our prior clinical opinion is worth 20% of the weight we will place on the new data. This gives the prior parameters $a = 1.2$, $b = 4.8$. Hence when we make decisions about stopping the study, the data from the study will dominate over the prior opinion.

The following table summarizes the threshold numbers for the stop rule boundary, which would lead to a recommendation to stop the study due to the excess 30-day mortality.

Number of subjects in the "overexpansion of bioprosthetic stratum"	Stop if the number of deaths within 30 days reaches
3-5	3
6-8	4
9-12	5
13-16	6
17-20	7
21-24	8
25-28	9
29-30	10

We investigated the performance of the above stopping rule by a simulation study. In each simulation run, we generated a study with 30 independent Bernoulli trials, each with a true certain 30-day mortality, and compared these outcomes with the above stopping boundary to determine whether the study was stopped. We repeated the simulation 100,000 times and computed the proportion of stopped studies using the above stopping rule. The following table summarizes the performance of this stopping rule:

True 30-day mortality rate	10%	15%	20%	25%	30%	35%	40%
Proportion of Stopped Studies (%)	1.6%	6.9%	18.9%	38.3%	60.5%	78.5%	90.5%
Average number of subjects	29.6	28.7	26.7	23.6	19.7	16	12.7
Average number of 30-day mortality	3	4.3	5.3	5.9	5.9	5.6	5.1

These simulation results suggest that our stopping rule has a low probability stopping a study when the true 30-day mortality rate is 20% or less, and the probability of stopping a study is high when the true 30-day mortality rate exceeds 20%. There, we believe that our Bayesian stopping rule for 30-day mortality has satisfactory statistical properties.

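### Sections 10.3.2 and 10.3.3 call the chance of stopping high once 30-day mortality exceeds the limit, but their own tables give 38–39% at 5 points over and about 80% only at 15 points over

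*Combined protocol and SAP*

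**What the plan says.** Section 10.3 sets separate stopping rules according to whether the operator intends to over-expand the bioprosthesis.

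- **No overexpansion (10.3.2).** "The stopping boundary is reached if the posterior probability that the 30-day mortality rate exceeds 15% is at least 90" per cent. The prior is Beta(0.9, 5.1). For true mortality of 10, 15, 20, 25, 30 and 35%, the results row reads: "Proportion of Stopped Studies 4.8% 17.3% 39% 62.3% 81.3% 92.2" per cent.
- **Overexpansion (10.3.3).** "The stopping boundary is reached if the posterior probability that the 30-day mortality rate exceeds 20% is at least 90" per cent. The prior is Beta(1.2, 4.8). For true mortality of 10, 15, 20, 25, 30, 35 and 40%, the row gives 1.6, 6.9, 18.9, 38.3, 60.5, 78.5 and 90.5%.

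Both simulations generate 30 subjects. Each section then draws its conclusion: "and the probability of stopping a study is high when the true" rate is above 15% in 10.3.2, and "the probability of stopping a study is high when the true 30-day mortality rate exceeds 20" per cent in 10.3.3. On that basis each section calls the rule's statistical properties satisfactory. Crossing a boundary in either stratum leads to a recommendation to stop the study.

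Section 10.1 recruits "until 30 subjects undergo attempted BASILICA TAVR in this protocol", so 30 is the total for both strata together.

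**The concern.** The concluding sentence carries no qualifier: it claims a high chance of stopping for any excess over the limit. At the first tabulated excess, 5 points, the probability is below one half in both strata, so such a stratum would more often run to 30 subjects than stop.

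The printed figures also apply only if all 30 subjects fall in one stratum. Once both strata are populated, neither table describes the rule as it will operate, and no figures are given for the trial as a whole.

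The limits come from section 10.3.1, where they are presented as the clinically acceptable 30-day mortality, and these rules are the trial's quantitative mortality safeguard. A board member who relied on the sentence could take an uncrossed boundary as evidence that mortality is within the limit. The rule cannot show that.

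**Working it through.** **Inputs.** Boundary tables, priors, 90% threshold and stopping probabilities from 10.3.2 and 10.3.3; total of 30 from 10.1. The split between strata is not in the documents, so stratum sizes below 30 are assumptions, shown as a range.

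**Step 1: boundaries.** For each n from 1 to 30, find the smallest number of deaths d with P(p > p0 | Beta(a + d, b + n − d)) ≥ 0.90. Using (p0, a, b) = (0.15, 0.9, 5.1) and (0.20, 1.2, 4.8), both printed tables match at every n.

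**Step 2: stopping probabilities with 30 subjects.** Let π_n(d) be the probability of having d deaths after n subjects without having stopped. Then π_n(d) = p·π_{n−1}(d−1) + (1−p)·π_{n−1}(d). Whenever d reaches the boundary for n, that mass moves to the stopping probability S. Exact results, with the protocol's figure in brackets:

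| Excess over limit | 15% rule | 20% rule |
|---|---|---|
| +5 points | 38.9% (39%) | 38.5% (38.3%) |
| +10 | 62.4% (62.3%) | 60.2% (60.5%) |
| +15 | 81.0% (81.3%) | 78.5% (78.5%) |
| +20 | 92.2% (92.2%) | 90.5% (90.5%) |

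All 13 printed probabilities reproduce within 0.4 points. At +5 the study goes unstopped about 100 − 39 = 61% of the time.

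**Step 3: smaller strata, each stratum's own boundary.**

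| Subjects in stratum | 15% rule: +5, +10, +15 | 20% rule: +5, +10, +15 |
|---|---|---|
| 10 | 16.8, 28.0, 40.9% | 16.2, 25.8, 37.1% |
| 15 | 24.2, 40.1, 56.6% | 24.0, 38.4, 53.8% |
| 20 | 30.1, 49.4, 67.6% | 31.0, 49.0, 66.5% |

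One entry can be checked by hand. With 5 subjects under the 20% rule, stopping needs 3 deaths. At true mortality 25% that is 10(0.25³)(0.75²) + 5(0.25⁴)(0.75) + 0.25⁵ = 0.0879 + 0.0146 + 0.0010 = 10.4%, the recursion's value.

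**Step 4: either boundary stops the trial.** With independent strata, P(either) = 1 − (1 − S₁)(1 − S₂), where S₁ is the stopping probability under the 15% rule and S₂ under the 20% rule. For a 15/15 split with both strata at +5: 1 − (1 − 0.242)(1 − 0.240) = 42.4%.

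| Split (no overexpansion / overexpansion) | Both +5 | Both +15 | Only overexpansion +5, other at limit |
|---|---|---|---|
| 10/20 | 42.6% | 80.2% | 36.6% |
| 15/15 | 42.4% | 80.0% | 32.7% |
| 20/10 | 41.4% | 79.6% | 27.9% |
| 25/5 | 41.7% | 81.2% | 24.7% |

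The last column uses S₁ at true mortality 15% (8.2, 11.5, 14.1 and 16.0% for 10, 15, 20 and 25 subjects) and S₂ at 25%. For example, 10/20 gives 1 − (1 − 0.082)(1 − 0.310), about 37%.

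These calculations, like the protocol's simulation, treat each 30-day outcome as known before the next subject is treated.

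**The case against.** The strongest reply has four parts.

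- **The aim is to detect a substantial excess.** Both sections open by saying that mortality should not go substantially above the anticipated rate, and the word high is never defined. Against that aim, 78–92% at 15 to 20 points over can fairly be called high. This stands as a defence of the rule. It does not rescue the sentence, which drops the qualifier; no ordinary reading of high covers 38–39%.
- **The figures are disclosed.** The full table stands directly above each sentence, so boards are not misled about the 30-subject case if they read it. This stands and limits the harm. It does not cover the case where the strata share 30 subjects, for which nothing is given.
- **Smaller strata do not weaken the trial-level safeguard when both run over.** A reader might infer from Step 3 that the trial's chance of stopping falls to 16–24%. The documents do not support that, because either boundary leads to a recommendation to stop the study. If both strata are equally over, the trial-level probability is about the same as, or slightly above, the printed rows. The reduction is per stratum, and reaches the trial level when only one stratum is over.
- **There are other safeguards.** Section 10.3 lets the safety board recommend termination without a boundary being crossed, and section 10.2.5 has deaths adjudicated independently. This stands. A board exercising judgement still needs a correct account of what the formal rule detects.

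**Conclusion.** The concern holds as a misdescribed operating property. A reader might infer that the tables or boundaries are miscalculated; they are not, since all of them reproduce. A reader might also infer that the protocol treats an uncrossed boundary as proof of acceptable mortality. It nowhere says so; that is a misreading which the present wording invites.

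With 30 subjects in one stratum, the chance of stopping is below one half at 5 points over the limit and near 80% only at 15 points over. If both strata are populated, each stratum's own rule detects less than its table shows. The trial-level probability is 41–43% when both are 5 points over, and about 25–37% when only the overexpansion stratum is 5 points over and the other is at its limit.

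The 30-subject figures are the protocol's own. The remaining figures rest on assumed splits from 10/20 to 25/5, independent strata and immediately known outcomes. The point should be corrected, but it does not call the rule itself into question.

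**What to change.** 1. In both 10.3.2 and 10.3.3, replace the concluding sentence with the figures: with 30 subjects in the stratum, stopping probability is about 39% at 5 points over the limit, 60–62% at 10 over, and about 80% only at 15 over.
2. Add operating characteristics for stratum sizes summing to 30, for example 10/20, 15/15 and 20/10. Show each stratum's own stopping probability and the probability that either boundary stops the trial, including the case where only one stratum is over its limit. Per-stratum rows alone would give a partial picture.
3. State that not reaching a boundary does not establish that 30-day mortality is at or below the limit.

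Boundaries, priors, the 90% threshold and the sample size stay as they are. The work is a reworded sentence in each section, one added statement and some extra table rows. The only cost is that the stated property becomes less favourable.
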